We will conduct an observational pre/post study to evaluate the impact of these efforts to optimize oxygen delivery and oxygenation in critically ill trauma patients.

Hypotheses:

[figure not shown]
We hypothesize that the clinical efforts to improve adherence to oxygen guidelines will:

- a) improve the proportion of time spent with target normoxia thresholds (oxygen saturation [SpO_2] 90-96%) by
- b) reducing utilization of unnecessary supplementation oxygen
- c) without a substantive increase in hypoxic episodes or an adverse impact on clinical outcomes.

II. Background and Significance:

Oxygen therapy has undisputed importance in the care of critically ill medical and trauma patients to treat and prevent morbidity associated with hypoxia.^{1,2} However, generous supplemental oxygen is routine, and often results in hyperoxia.³⁻⁶ While there is no known benefit of excessive oxygenation, common clinical perception has been that this practice is safe and creates a margin of safety against hypoxia.⁷⁻⁹ However, evidence indicates that hyperoxia can also harmful. Here we summarize the rationale and relevance of the proposed research to avoid but hypoxia and hyperoxia and target normoxia.

[figure not shown]
Pre-clinical and observational data support the concept of targeted normoxia. There is a U-shaped relationship between oxygenation and mortality in critically ill patients, with both ends of the spectrum—hypoxia and hyperoxia—individually associated with higher mortality.^{10,11} Laboratory evidence has long demonstrated toxicity associated with hyperoxia through mitochondrial production of pro-inflammatory reactive oxygen species

ischemic vasoconstriction that leads to tissue damage and vital organ injury.¹²⁻¹⁴ **Figure 1** summarizes the underlying cellular mechanisms for balance between the beneficial and harmful effects of oxygen therapy.

Figure 1. Beneficial (green arrows) and deleterious (red arrows) effects of oxygen therapy during circulatory shock. *Adapted from Asfar P et al. Intensive Care Med 2015;41:1118.*

[figure not shown]
Numerous observational cohort studies have demonstrated an association between hyperoxia and higher mortality broadly in intensive care unit patients and in specific subpopulations, such as cardiac arrest, myocardial infarction, ischemic stroke, and

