We conducted a Delphi consensus process enlisting panel of 31 national and local experts in trauma surgery, critical care and emergency medicine.

We asked the expert panel to rate how strongly they agreed or disagreed with specific SpO2 low thresholds, SpO2 high thresholds, PaO2 low thresholds and PaO2 high thresholds. Based off our analysis of the data, we were able to identify what the majority of experts felt were appropriate oxygenation thresholds. Initial votes are summarized in Figures 4-7 below.

Figure 4: Agreement with Lower SpO2 Thresholds in Delphi Stage 2

[figure not shown]

Figure 5: Agreement with Higher SpO2 Thresholds in Delphi Stage 2

Figure 6: Agreement with Lower PaO2 Thresholds in Delphi Stage 2

[figure not shown]
[figure not shown]

Figure 7: Agreement with Higher PaO2 Thresholds in Delphi Stage 2

For these data, we proposed an SpO₂ range of 90-96%, PaO₂ range of 60-100 mmHg. In the Final Delphi Stage, we asked our expert panel for a final yes/no vote on these thresholds to confirm final consensus on oxygenation in critically ill trauma patients. Voting was as follows, which confirmed our final target ranges (>80% agreement was pre-defined as consensus):

- ▶ Low SpO₂ threshold = 90%
 - 89% agreement
- ▶ High SpO₂ threshold = 96%
 - 89% agreement
- ▶ Low PaO₂ threshold = 60 mmHg
 - 96% agreement
- ▶ High PaO₂ threshold = 100 mmHg
 - 89% agreement

These thresholds are concordant with existing clinical guidelines at University of Colorado Hospital, and the data from the expert consensus process has provided additional motivation for clinical leadership to improve their adherence to guidelines. In an observational study design, we will evaluate the impact of clinical efforts to improve guideline adherence.

III. Research Methods

A. Outcome Measure(s):

For the primary feasibility outcome, we will assess oxygenation, as measured by SpO₂ and PaO₂, relative to amount of supplementation oxygen during the first 7 days. For ventilated

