patients, supplemental include fraction of inspired oxygen (FiO_2), positive end expiratory pressure, ventilator mode, mean airway pressure, and tidal volume. With this information we can calculate both P/F ratio and oxygenation index. For non-ventilated patients, we will collect volume and route of supplemental oxygen. These data will be used to longitudinally calculate the observed oxygenation compared to the defined oxygenation targets (SpO_2 90-96% and PaO_2 60-100 mmHg). In addition, we will calculate the duration of hyperoxia time ($\text{SpO}_2 > 96\%$ or $\text{PaO}_2 > 100$ mmHg, unless no supplemental oxygen is delivered), and number/duration of hypoxia episodes ($\text{SpO}_2 < 88\%$ or $\text{PaO}_2 < 60$ mmHg, unless FiO_2 is 100%).

Although this pilot study will be underpowered for clinical outcomes, we will measure in-hospital mortality, ventilator-free days, duration of supplemental oxygen, acute organ injury (as measured by daily Sequential Organ Failure Assessment [SOFA] scores over 7 days), intensive care unit length of stay, hospital length of stay, and hospital disposition (facility vs. home).

B. Description of Population to be Enrolled and C. Study Design and Research Methods

We will conduct a pilot study to inform a future larger scale implementation study across multiple trauma centers to test the clinical effectiveness of the targeted normoxia strategy. In the proposed pilot study, we will test and optimize feasibility and potential for effectiveness.

Study Design and Setting: This study will be an observational before-after study conducted at the University of Colorado Hospital.

Participants: We will compare oxygenation and outcomes trauma patients admitted to the ICU during the 6 months after the clinical implementation to similar patients during the same 6 months in the prior year (to adjust for seasonal effects) and the immediate preceding 6 month period (to minimize potential for secular trends).

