Electronic data will be stored on University servers or on password-protected/encrypted computers that are behind the University firewall. We do not anticipate any hard copy data, but should be generated, they will be secured in a locked file cabinet in a locked office. Data will be stored for as long as IRB and DOD regulations recommend, whichever is longer (typically 5 years). A limited de-identified dataset will be archived long-term for future use by the local investigators and the general research community. The proposed research does not interface with the FDA, and thus, there are no special requirements relating to disposition of data.

E. Potential Scientific Problems:

The biggest challenge to the research will be the extent to which guideline adherence is improved during the study period.

There can also be challenges with electronic data collection with Health Data Compass. However, we have worked closely with Compass in the preparatory work (COMIRB #17-1359), and also will supplement electronic data collection with manual chart review as needed.

F. Data Analysis Plan:

We will model continuous SpO₂ and PaO₂ data separately and a third model where both are combined. The SpO₂ model will have the most field relevance but incorporating the PaO₂ data will be useful in applying results to the hospital setting in future implementation trials. Specific attention will be paid to the defined normoxia target range, as well as short-term episodes of hypoxia or hyperoxia. Oxygenation and oxygen supplementation data will be analyzed descriptively.

Clinical outcomes will be analyzed descriptively to compare the pre- and post-periods. We will also adjust for a limited number of covariates (eg, injury severity) to reduce risk of confounding. However, we fully recognize that the primary purpose of this pilot intervention is feasibility and safety, and so clinical outcomes will be underpowered.

G. Summarize Knowledge to be Gained:

The proposed pilot study will help us to understand the feasibility, barriers, and facilitators for improving oxygenation practices in critically ill trauma patients. The results will provide valuable preliminary data for planning a large multicenter implementation trial to evaluate the impact of this intervention on clinical outcomes and safety. These data collectively will provide actionable data to improve care of critically injured civilians and military service members.

H. References:

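### Time with SpO₂ in 90-96%, the subject of hypothesis (a), is not the response of any stated model and has no stated adjusted pre/post estimate or interval

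*Combined protocol and SAP*

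**What the plan says.** Section I (Hypotheses and Specific Aims) describes the study this way: "We will conduct an observational pre/post study to evaluate the impact of these efforts to optimize oxygen delivery and oxygenation". Hypothesis (a) is that the effort will "improve the proportion of time spent with target normoxia thresholds", given there as SpO₂ 90-96%. Hypothesis (c) adds that hypoxic episodes should not rise substantively.

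Under Research Methods, section A (Outcome Measures), the primary feasibility outcome is oxygenation, by SpO₂ and PaO₂, "relative to amount of supplementation oxygen during the first 7 days". The data will be used to "longitudinally calculate the observed oxygenation compared to the defined oxygenation targets". Two further measures are defined:

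- For hyperoxia, "we will calculate the duration of hyperoxia time", meaning SpO₂ above 96% or PaO₂ above 100 mmHg, except when no supplemental oxygen is given.
- For hypoxia, "number/duration of hypoxia episodes", meaning SpO₂ below 88% or PaO₂ below 60 mmHg, except at FiO₂ 100%.

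The participants paragraph (sections B and C) says oxygenation and outcomes in the 6 months after implementation will be compared with the same 6 months a year earlier and with the 6 months immediately before.

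Section F (Data Analysis Plan) then says "We will model continuous SpO₂ and PaO₂ data separately and a third model where both are combined". It promises particular attention to the target range and to short episodes outside it, and adds: "Oxygenation and oxygen supplementation data will be analyzed descriptively". A separate paragraph covers clinical outcomes. That paragraph holds the only pre/post comparison named in section F, followed by the only mention of covariate adjustment.

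**The concern.** The quantity in hypothesis (a) is a proportion of time between two bounds. Section F never makes that proportion the response of a model. It names no effect measure for the change in it, and does not say that the change will be adjusted or reported with an interval.

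Three things are at stake. First, the periods are not randomised, so a difference in injury severity between them could appear as a change in oxygenation practice. Second, the results are meant to inform a multicentre implementation trial, which needs an effect estimate with its uncertainty. Third, the analyst would have to choose the denominator, the comparator period, the treatment of time without supplemental oxygen and the method after the data are in hand.

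The combined model adds a smaller problem. It joins a percentage and a pressure in mmHg, and no outcome for it is defined.

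**Working it through.** The plan gives no sample size, effect size, SD or power for oxygenation, so there is no figure to reproduce. The check has three parts.

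**1. Hypothesis against analysis**

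| Element needed to estimate hypothesis (a) | Where the plan stands |
|---|---|
| Variable: proportion of time in 90-96% per patient | In hypothesis (a); section A calculates oxygenation against target but does not define this proportion |
| Comparison: post against pre | In the participants paragraph, for oxygenation generally; not in section F for oxygenation |
| Effect measure and interval | Not stated |
| Adjustment for case mix | Stated after clinical outcomes; not clearly extended to oxygenation |
| Model response | Not stated for any of the three models |

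**2. Would a model of mean SpO₂ supply the answer?** This is an illustration. All means and SDs are assumptions. Readings are taken as normal with mean μ and SD σ, rounded to whole percentages and capped at 100. Then

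- share in 90-96 = Φ((96.5 − μ)/σ) − Φ((89.5 − μ)/σ)
- share below 88 = Φ((87.5 − μ)/σ)

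Pre-period, μ = 97.5, σ = 2: Φ(−0.5) − Φ(−4) = 30.8% in range. The mean after capping is 97.4.

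Post-period, μ = 95.5:

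| σ | In 90-96 | Gain on 30.8% (points) | Below 88 | Mean after capping | Fall in mean |
|---|---|---|---|---|---|
| 2 | Φ(0.5) − Φ(−3) = 69.0% | 38.2 | 0.0% | 95.5 | 1.9 |
| 3 | Φ(0.333) − Φ(−2) = 60.8% | 30.0 | 0.4% | 95.4 | 2.0 |
| 4 | Φ(0.25) − Φ(−1.5) = 53.2% | 22.4 | 2.3% | 95.2 | 2.2 |
| 5 | Φ(0.2) − Φ(−1.2) = 46.4% | 15.6 | 5.5% | 95.0 | 2.4 |

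Falls in the mean of 1.9 to 2.4 points therefore go with gains of 15.6 to 38.2 points.

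The result does not depend on the normal shape. With a beta distribution on 80-100% and the mean held at 95, time in range is 94%, 75%, 58% and 44% for SDs of 1, 2, 3 and 4.

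The two-sided bound matters even with the SD fixed. Normal means of 91 and 95, both with SD 2, give the same 77.0% in range: Φ(2.75) − Φ(−0.75) and Φ(0.75) − Φ(−2.75). Time below 88 is 4.0% at mean 91 and about 0% at mean 95.

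**3. Can time in range be recovered from the hyperoxia and hypoxia measures?** No. SpO₂ of 88-89% is below target but not hypoxic by section A's SpO₂ definition. Under the beta illustration this band holds 0.7% of time at mean 95, SD 2, and 9.8% at mean 93, SD 4. SpO₂ above 96% without supplemental oxygen is outside 90-96% but is not counted as hyperoxia. Subtracting the two durations from total time does not leave time in range.

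**The case against.** A reader might infer that the plan models mean SpO₂ and so aims at the wrong quantity. The documents do not support that. Section F speaks of continuous data, which may mean the continuously recorded 7-day series, and it states no response or model form. The models are unspecified; they are not shown to be models of a mean.

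A reader might also infer that no comparison of oxygenation against target is planned at all. That too goes beyond the text. The outcome section calculates oxygenation against the targets, the participants paragraph compares oxygenation across periods, and section F gives attention to the range. Together these imply a descriptive pre/post look, and a descriptive estimate is still an estimate.

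Nor would a rise in hypoxia go unseen. Hypoxia and hyperoxia are measured separately, and section F names them for attention.

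The illustration has limits as well. Most of its spread comes from letting the SD rise after implementation while the pre-period SD stays at 2. With SD 2 in both periods, only the first row of the table applies. The randomised pilot trial described in the Background had 0.3% and 1% of time below 88% in its two arms, far below the 5.5% in the last row.

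All of these points stand. They do not supply a defined endpoint, an adjusted contrast or an interval for hypothesis (a). The caveat about low power does not cover the omission either, since it is made for clinical outcomes.

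**Conclusion.** The point holds as a specification gap. The plan implies a descriptive look at oxygenation against target. It does not make time in 90-96% the response of a stated model, and does not say that its pre/post change will be adjusted or given an interval. In a non-randomised before-after study, that leaves the main result open to case-mix differences and its precision unreported.

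The size of any resulting error cannot be derived from the documents. The range of 16 to 38 points shows only that a mean does not determine time in a two-sided range, and it rests wholly on assumed distributions and SDs. The conclusion about the missing estimate rests on the text alone and does not depend on those figures. The change is worth making before analysis, though the study's descriptive pilot purpose means that nothing already calculated is wrong.

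**What to change.** Amend section F as follows.

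- **Primary measure.** Each patient's proportion of SpO₂-monitored time in 90-96% over the first 7 days. State the denominator and how readings are time-weighted.
- **Primary estimate.** The post-minus-pre difference in that proportion with a 95% CI, from a patient-level regression for proportions (for example fractional logit with robust standard errors), adjusted for injury severity and other named baseline covariates. One value per patient removes the dependence between repeated readings.
- **Comparators.** Give the estimate against each of the two pre-periods in the participants paragraph.
- **Time above 96% without supplemental oxygen.** Keep hypothesis (a)'s plain 90-96% definition as primary. Add a sensitivity analysis that removes this time from the denominator. The outcome section exempts it from hyperoxia only, so its handling here has to be stated.
- **Alongside.** Report hypoxia and hyperoxia time by period, so that a gain in range can be read against hypothesis (c).
- **Other models.** Keep the continuous SpO₂ and PaO₂ models as secondary and state their response. Define the combined model on in-range status, or drop it.

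The cost is plan wording and one extra model on data already being collected. The small downside is that the continuous models become secondary.

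### The only covariate adjustment in the analysis plan sits with the clinical outcomes, so the primary pre/post oxygenation comparison is left open to case-mix bias

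*Combined protocol and SAP*

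**What the plan says.** Hypothesis (a) in section I is a rise in the proportion of time spent at SpO₂ 90-96%. The Outcome Measure(s) section makes this domain primary: "For the primary feasibility outcome, we will assess oxygenation". The Participants paragraph commits to comparing both oxygenation and outcomes across periods. It compares ICU trauma admissions "during the 6 months after the clinical implementation to similar patients during the same 6 months in the prior year" and also to those in "the immediate preceding 6 month period (to minimize potential for secular trends". The prior-year period is there for season. No matching or weighting rule says what makes patients similar.

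Section F has two analysis paragraphs. The oxygenation paragraph begins "We will model continuous SpO₂ and PaO₂ data separately and a third model where both are combined" and ends "Oxygenation and oxygen supplementation data will be analyzed descriptively". The clinical-outcomes paragraph begins "Clinical outcomes will be analyzed descriptively to compare the pre- and post-periods", continues "We will also adjust for a limited number of covariates (eg, injury severity) to reduce risk of confounding", and ends by noting that clinical outcomes will be underpowered.

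**The concern.** In a before-after study without randomisation, the crude difference mixes the effect of the educational effort with any difference in who was admitted. The cohort is mixed by design: it spans surgical-trauma and neurosurgical ICUs, and ventilated and non-ventilated patients. The plan accepts that confounding needs adjustment, but attaches that adjustment most plainly to the outcomes it calls underpowered, not to the one its main hypothesis concerns.

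The stated aim is to evaluate the impact of the effort and to inform a multicentre trial. Section E warns: "The biggest challenge to the research will be the extent to which guideline adherence is improved during the study period". If adherence improves only a little, a given case-mix shift takes up a larger part of the observed difference.

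**Working it through.** **1. What the text commits to.**

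| Element | Oxygenation (primary) | Clinical outcomes |
|---|---|---|
| Between-period comparison stated in Participants | yes | yes |
| Pre/post comparison restated in section F | no | yes |
| Model announced in section F | yes, without form, period term or covariates | no |
| Descriptive analysis stated | yes | yes |
| Covariate adjustment | none in its paragraph | yes, injury severity as the example |

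The adjustment sentence names no outcome, so it could be read to cover oxygenation. Its position between two clinical-outcome sentences favours the narrower reading.

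**2. What the design controls.** The hospital and ICUs are constant, and the two earlier periods address season and secular trend. Neither period controls injury severity, ventilation status or ICU type.

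**3. Size of a possible bias.** The documents give no sample size, SD or case-mix figures, so there is no figure to reproduce. Every input from here on is an assumption. With no true effect and one binary factor:

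bias = (post share − comparator share) × (gap in mean time on target between the two groups)

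| Shift in share | Gap 10 points | Gap 20 points | Gap 30 points |
|---|---|---|---|
| 5 points | 0.5 | 1.0 | 1.5 |
| 10 points | 1.0 | 2.0 | 3.0 |
| 15 points | 1.5 | 3.0 | 4.5 |

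Entries are percentage points of time on target. The sign depends on the direction of the shift and of the gap.

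**4. Would the two comparators reveal it?** Assume time on target is 20 points lower if ventilated.

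| Ventilated share: prior year / preceding / post | Bias against prior year | Bias against preceding |
|---|---|---|
| 50 / 50 / 40% | (0.40 − 0.50) × (−20) = +2.0 | (0.40 − 0.50) × (−20) = +2.0 |
| 45 / 55 / 40% | (0.40 − 0.45) × (−20) = +1.0 | (0.40 − 0.55) × (−20) = +3.0 |
| 55 / 45 / 50% | (0.50 − 0.55) × (−20) = +1.0 | (0.50 − 0.45) × (−20) = −1.0 |
| 50 / 50 / 60% | (0.60 − 0.50) × (−20) = −2.0 | (0.60 − 0.50) × (−20) = −2.0 |

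In the first and last rows the comparators agree and the bias is hidden. In the third they disagree in sign, which could serve as a signal.

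**5. Against random error.** With an assumed SD of 25 points, SE = 25 × √(2/n). This is 2.5 points at n = 200 per period and 3.5 at n = 100. A 2-point bias at n = 200 is 2.0/2.5 = 0.8 SE. The plan states no test, but if a two-sided 5% test were run on the crude difference, a 2-point bias would raise its false-positive rate to 8.7%, 12.6% and 16.5% at n = 100, 200 and 300.

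**6. What adjustment does and costs.** A simulation (1000 runs, 200 per period, no true effect, fractional logit with four baseline covariates) used the 50/50/40 shares. Crude differences averaged +2.1 and +1.9 points, and adjusted differences +0.1 and −0.1. The SD was 2.6 crude and 2.4 adjusted. Because the model was given the planted confounder, this confirms the arithmetic and is not evidence of bias in this study.

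When case mix was equal and the covariates were unrelated to outcome, the SDs for the two contrasts were:

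| Patients per period | Crude | Adjusted |
|---|---|---|
| 200 | 2.49 / 2.41 | 2.49 / 2.42 |
| 100 | 3.56 / 3.62 | 3.57 / 3.64 |

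Unneeded adjustment therefore costs almost no precision on these inputs.

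**The case against.** The strongest reply is that this is an ambiguity and not an omission. The adjustment sentence is not limited to any outcome, oxygenation is to be modelled, and the Participants paragraph already states the period contrast. The plan nowhere says the contrast will be unadjusted. That is fair, but it shows only that adjustment may be intended. If it is, saying so settles the main point.

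Second, this is a feasibility pilot with no confirmatory test, and a descriptive summary can suit it. That also stands, and it limits the weight of the concern. It does not help a reader separate changed practice from different patients.

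Third, nothing shows that case mix shifted, and the real change may be large. Section I reports hyperoxia on supplemental oxygen for more than half of the hospitalization. A randomised trial cited in section II found 4% against 22% of time in the hyperoxic range, an 18-point gap. These figures show room for a change larger than the assumed bias. The trial randomised patients to oxygen targets, however, so it does not predict what education will achieve here.

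Fourth, the assumed 20-point deficit in ventilated patients has no support in the documents. Hypothesis (a) states no exception for patients above 96% without supplemental oxygen, although the hyperoxia definition does. The gap could therefore run the other way. The magnitude is given with either sign for this reason. The same feature suggests how case mix could matter: a change in how many patients need oxygen could move time on target without any change in practice.

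**Conclusion.** The concern holds. As written, the plan clearly commits only to a crude comparison for its primary outcome, while stating adjustment for the outcomes it calls underpowered. The reading of the text rests on the placement of one sentence, so confidence is medium. The calculated range of 0.5-4.5 points illustrates the mechanism and does not show that bias exists. At an assumed 200 patients per period, a 2-point bias lies within one standard error: a modest distortion, not a dominant one. The change should be made because it applies the plan's own principle to its main hypothesis at little cost. It is not a fatal defect.

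**What to change.** In section F:

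- Keep the descriptive summary, reconcile it with the sentence announcing models, and state that covariate adjustment also applies to oxygenation.
- Specify a patient-level model of the proportion of first-7-day time at SpO₂ 90-96%. Fractional logistic regression with robust standard errors is one suitable form.
- Enter period as three levels: post, same six months of the prior year, and immediately preceding six months.
- Adjust for a short list fixed at ICU admission: injury severity, age, ventilated at admission, and ICU type. Also show the result without ventilation at admission, because Emergency Medicine takes part in the education and could influence it.
- Do not adjust for FiO₂ or oxygen flow during the stay. Hypothesis (b) makes oxygen use the mechanism.
- Report crude and adjusted differences with 95% confidence intervals against each comparator, tabulate case mix by period, and say what similar patients means (for example, same eligibility only).

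How the outcome treats time without supplemental oxygen, and death or discharge before day 7, is a separate question of definition that should be settled in the same text.

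The cost is plan wording and a little analysis time. Injury severity is the plan's own example, ventilator data are already listed, and ICU type defines the cohort. The team must confirm that the covariates are in the extraction and derive age before date of birth is removed.
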